Study Protocol and Statistical Analysis Plan

for

RehabTouch: A Mixed-Reality Gym for Rehabilitating the Hands, Arms, Trunk, and Legs after Stroke

NCT03503617

Document Date: 08/31/2021

Trial Design

This study was a single-site, single-blind randomized controlled trial comparing home-based therapy with RehabTouch to conventional therapy for individuals in the subacute phase of stroke. RehabTouch is a commercial home rehabilitation technology (sold as FitMi® by Flint Rehab) designed to put into practice clinically recommended design features for at-home rehabilitation technology. The study was performed at Rancho Los Amigos National Rehabilitation Center in Downey, CA. Participants were invited for an initial assessment to confirm they met the inclusion criteria and to establish baseline measures. Participants provided informed written consent. Qualifying participants were randomly assigned to either the RehabTouch group or the conventional group. Participants in both groups were instructed to perform self-guided therapy for at least three hours/week for three consecutive weeks. All participants received weekly phone calls from a supervising therapist. After the three-week exercise period, participants returned for an end-of-therapy assessment. The trial was pre-registered on ClinicalTrials.gov (NCT03503617) and approved by the Rancho Research Institute, Inc. Institutional Review Board at Rancho Los Amigos National Rehabilitation Center (IRB #263).

Participants

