Inclusion criteria were: experienced one or more strokes between 2 weeks and 4 months prior; baseline UEFM Score >5 and ≤55 out of 66; absence of moderate to severe pain defined as a score of 4 or lower on the 10 point visual-analog pain scale; ability to understand the instructions to operate RehabTouch; and aged 18 to 85 years old, as older age could be a confounding variable. Exclusion criteria were: concurrent severe medical problems that precluded the individual from participating in routine rehabilitation; visual deficits defined as a score >1 on question 3 of the NIH Stroke Scale (NIHSS); severe cognitive deficits or apraxia defined as a score >0 on questions 1a and 1c of the NIHSS; severe neglect defined as a score >1 on question 11 of the NIHSS; severe aphasia defined as a score >1 on question 9 of the NIHSS; and enrollment in other therapy studies. Recruitment aimed to balance the age, ethnicity, and gender of the study participants to be representative of Los Angeles County in California, USA. All participants provided informed consent.

Using an estimated effect size of 1.05 based on long-term follow-up data from a previous arm training study during subacute stroke, [1] power analysis established that 21 participants in each group would provide a 90% chance of detecting a significant difference between RehabTouch and conventional therapy at the 0.05 significance level (two-tailed t-test). To account for 20% dropout, the target sample size was n = 25 participants in each group.

Adaptive randomization was used to ensure matched levels of impairment between the RehabTouch and conventional therapy groups. Specifically, subjects were stratified by their UEFM Score into three levels (i.e. 5-22, 23-39, 40-55) and then randomized by alternating block allocation.[2]

Intervention

Participants randomized to the RehabTouch group were given a RehabTouch system with the custom 10" touchscreen tablet. They received 30 minutes of training on how to set up and use the RehabTouch system. They were instructed to spend most of their time performing upper extremity exercises, but access to the trunk and leg exercises in the RehabTouch software was not disabled.

Participants randomized to the conventional therapy group were given a booklet of paper exercises that were selected from the same library of 40 exercises available in the RehabTouch software.

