For both groups, a supervising rehabilitation therapist selected the exercises for each participant based on their specific impairments. All participants received 30 minutes of training from the therapist on how to perform the selected exercises correctly.

After the 3-week exercise period, participants returned for an end-of-therapy assessment. At this assessment, participants returned the RehabTouch system or the sensorized booklet of exercises for data collection. Participants returned one month later for a follow-up assessment.

Outcomes

The primary outcome measure was the change in Upper Extremity Fugl-Meyer (UEFM) score[3] from baseline assessment to one-month follow-up. UEFM was assessed at baseline, end-of-therapy, and one-month follow-up. Secondary measures included the Box and Blocks Test,[4] the 10 Meter Walk Test,[5] the Modified Ashworth Spasticity (MAS) scale[6] for the elbow, wrist, and fingers, and the Visual Analog Pain (VAP) scale for the upper extremity, all of which were assessed at baseline, end-of-therapy, and one-month follow-up. Motor Activity Log (MAL) was measured at end-of-therapy and one-month follow-up to assess self-reported quantity and quality of movement.[7] The European Quality of Life five dimensions, three levels (EQ-5D-3L) and its companion Visual Analog Scale (EQ-VAS) were measured at end-of-therapy and at one-month follow-up to assess overall perceived health state,[8], [9] and the Intrinsic Motivation Inventory (IMI)[10] categories of Interest/Enjoyment, Value/Usefulness, and Effort/Importance were measured at end-of-therapy to assess participants' perceived motivation. These measures are widely used in stroke rehabilitation research and have good sensitivity and reliability. All assessments were performed by a blinded, trained evaluator.

To assess adherence, the RehabTouch software recorded the date, time, and number of repetitions completed for each exercise, and the exercise booklet was placed in a sensorized folder that measured the times at which the participants opened the booklet.

Statistical Methods

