Statistical analyses were performed using Matlab R2020 software. Change in UEFM score from baseline assessment to one-month follow-up was compared between the RehabTouch group and conventional therapy group using an unpaired two-tailed t-test. Three participants in the conventional therapy group did not perform their one-month follow-up assessment; one of these did perform the end-of-therapy assessment. For this one participant, the missing one-month follow-up data point was imputed for the primary outcome measure by adding the average change in UEFM score across all participants in the conventional therapy group from end-of-therapy to one-month follow-up to this participant's end-of-therapy UEFM score. All other analyses were performed using only data from participants who completed all three assessments.

MAS scores were grouped by flexion or extension items and summed to obtain lumped MAS extension and flexion values. We quantified items marked with a '+,' with an additional 0.5 points for calculations. EQ-5D-L3 was analyzed following.[8], [9] IMI categories were compared across groups using Wilcoxon rank sum tests. For the secondary outcomes with baseline assessments, differences between groups at baseline and at one-month follow-up were assessed using unpaired, two-tailed t-tests. Within group changes from baseline to end-of-therapy and baseline to one-month follow-up were compared using paired, two-tailed t-tests. For the secondary scores were compared to one-month follow-up scores using paired, two-tailed t-tests.

To assess the ability of RehabTouch to motivate an appropriately high dose of home therapy, we performed a post-hoc exploratory analysis comparing the total number of repetitions that RehabTouch participants completed to a theoretical target dose of 2,700 repetitions. A dose of 2,700 repetitions of UE exercise corresponds to 300 repetitions/hour (5 reps/minute) over 9 hours of exercise, an intensity and duration sufficient to provoke a forelimb rehabilitative effect in a rodent model of stroke.[11]

Certain participants were missing data at one or more time points for the secondary outcomes MAS, VAP and IMI. If a participant's record for a given measure was missing data, that participant was omitted from any analysis for that measure. Thus, for MAS calculations (RehabTouch n=13 and conventional n=8), for VAP analysis (RehabTouch n=12 and conventional n=9), and for IMI analysis (RehabTouch n=13).

Interim Analysis

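### The post-hoc dose analysis sets an all-exercise repetition total against a target defined for upper-extremity repetitions only

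*Combined protocol and SAP*

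**What the plan says.** The Statistical Methods section describes a post-hoc exploratory analysis in the RehabTouch group, "comparing the total number of repetitions that RehabTouch participants completed to a theoretical target dose of 2,700 repetitions". Its purpose is to judge whether the device motivates enough home exercise. The following sentence defines the target: "A dose of 2,700 repetitions of UE exercise corresponds to 300 repetitions/hour (5 reps/minute) over 9 hours of exercise". The justification given is rodent stroke work on the forelimb.

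Other parts of the document bear on what a total might contain:

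- The title presents the system as "A Mixed-Reality Gym for Rehabilitating the Hands, Arms, Trunk, and Legs after Stroke".
- Under Intervention, on the RehabTouch group: "They were instructed to spend most of their time performing upper extremity exercises". The same sentence adds that "access to the trunk and leg exercises in the RehabTouch software was not disabled".
- Also under Intervention, for both groups: "a supervising rehabilitation therapist selected the exercises for each participant based on their specific impairments".
- Under Outcomes, the adherence paragraph says the software recorded the date, time and "number of repetitions completed for each exercise".

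**The concern.** The two sides of the comparison are in different units. The target is specific to the upper limb, in its definition and in its rationale. The quantity set against it is a total with no stated restriction to the upper limb. The document also describes how non-UE repetitions could arise: trunk and leg exercises were open to participants, and the instruction asked for most of the time on the arm, not all of it.

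Any trunk or leg repetition in the total raises the apparent dose without adding to the UE dose that the target describes. The error can therefore run in one direction only, towards a more favourable picture of the device. At stake is the reading of an exploratory statement about dose. No test of efficacy depends on it.

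**Working it through.** **Inputs.** From Statistical Methods: 5 repetitions per minute, 300 per hour, 9 hours, target 2,700. From Trial Design: at least 3 hours per week for 3 weeks. The non-UE share of repetitions, s, is not in the document. The values of s below are assumptions. They are not derived from the instruction on exercise mix, which concerns time and not repetitions.

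**The plan's own figure.** 5 × 60 = 300 repetitions per hour; 3 × 3 = 9 hours; 300 × 9 = 2,700. The target reproduces exactly and is not in question.

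**Effect of counting non-UE repetitions.** If a share s of a total T is trunk or leg work:

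- UE repetitions = T × (1 − s)
- total at which the UE count reaches the target = 2,700 / (1 − s)
- factor by which the total overstates the UE dose = 1 / (1 − s)

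| Assumed s | UE repetitions when T = 2,700 | UE repetitions per hour over 9 h | Total needed for 2,700 UE repetitions | Overstatement factor |
|---|---|---|---|---|
| 0% | 2,700 | 300 | 2,700 | 1.00 |
| 10% | 2,430 | 270 | 3,000 | 1.11 |
| 25% | 2,025 | 225 | 3,600 | 1.33 |
| 40% | 1,620 | 180 | 4,500 | 1.67 |

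For example, at s = 25%: 2,700 × 0.75 = 2,025; 2,025 / 9 = 225; 2,700 / 0.75 = 3,600; 1 / 0.75 = 1.33.

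**When it would matter.** A total falls on the wrong side of the target only if it is at least 2,700 but below 3,000, 3,600 or 4,500, for s of 10%, 25% or 40%. At s = 0, or for totals outside that range, the conclusion is the same under either count. The same arithmetic holds for a group mean, with s taken as the share in the pooled repetitions. The hourly column assumes exactly 9 hours of exercise; the document sets a minimum and does not give the time achieved.

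**The case against.** The best reply is that this is loose wording and not an analysis error. The sentence naming the comparison is followed at once by one that describes the same 2,700 as UE repetitions, so the UE meaning may have been intended throughout. Participants were enrolled on an arm-impairment score, exercises were chosen by a therapist, and the instruction favoured the arm, so the non-UE share may have been small. The stated purpose refers to home therapy in general, for which an all-exercise total is a reasonable measure. The document also sets no rule for classing a participant as having met the target, so the ranges in the calculation illustrate a threshold that the plan does not formally apply.

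Much of this stands. A UE-only count is a possible reading, and the document does not show that any trunk or leg repetition was performed or counted. The shares are assumed, and the ranges show only what being above or below the stated target would mean.

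Two things remain. The therapist's selection is not limited to arm exercises, so the protocol does not rule out non-UE repetitions. And a general aim may justify reporting an all-exercise total, but it does not make that total comparable with a target defined for the upper limb.

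**Conclusion.** The concern holds as a minor point. As written, the analysis names a quantity that does not match its benchmark, and any resulting error favours the device. The size cannot be determined from the document. It is zero if the count was restricted to UE exercises or if no trunk or leg repetitions were done, and under the assumed shares of 10% to 40% the total would overstate the UE dose by a factor of 1.11 to 1.67. The finding rests on the literal wording and on the absence of any restriction elsewhere in the document. It does not touch the change in UEFM score, the comparison between groups, the sample size or the interim analysis.

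**What to change.** Count each RehabTouch participant's upper-extremity repetitions from the per-exercise log and compare that count with the unchanged 2,700. Report trunk and leg repetitions, or the all-exercise total, separately as a measure of adherence. If the total was already limited to UE exercises, say so in the sentence that defines the comparison.

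No new data are needed, because repetitions were logged by exercise. The work is to label the exercises in the 40-exercise library as UE, trunk or leg (the document does not list them), apply a filter, and change one sentence. The only other cost is that the reported dose may look less favourable. The target, the instructions to participants and all other analyses stay as they are.
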